11.4 Sensitivity analyses

To determine the robustness of the analysis of the primary endpoint, we will perform sensitivity analyses with imputations for missing data. While we do not expect the trial intervention to affect dropouts, it is unreasonable to assume that dropouts will occur completely at random, and dropouts may therefore bias the results. We therefore aim to do best-case, worst-case, no-change scenario imputations for missing data:

- Scenario 1 (best-case): missing data in the intervention arm are imputed such that the change from baseline to 12 months is mean change 1 standard deviation (SD), whereas missing data in the placebo arm are imputed such that the change from baseline to 12 months is equal to the mean change. The mean change and SD are based on all observed values from both the intervention and placebo arms.
- Scenario 2 (worst-case): missing data in the intervention arm are imputed such that the change from baseline to 12 months is mean change + 1 SD, whereas missing data in the placebo arm are imputed such that the change from baseline to 12 months is equal to the mean change. The mean change and SD are based on all observed values from both the intervention and placebo arms.
- Scenario 3 (no-change): all missing data in intervention and placebo arms are imputed as the overall (i.e., both treatment arms combined) mean observed value at each time point

12 Safety Analyses and Adverse Events

Safety analyses will include tabulation of type and frequency of all adverse events. Any value of safety laboratory parameters outside normal ranges will be identified. The final report will include the absolute number of adverse and severe adverse events in each group. The results will be reported for the SS only.

Adverse events include

- Injection site reactions
- Infections
- Any event leading to discontinuation of study medicine
- Death
- Any rejection
- Treated rejections
- Renal event
- Cardiovascular events

Safety laboratory parameters include

- Creatinine > 3 times above upper limit of normal
- Total leucocyte count < 2.0x10⁹/L
- Creatinine kinase > 10 times above upper limit of normal
- ALT > 3 times upper limit of normal

Serious adverse events and adverse events of special interest (pregnancies) will be reported with comprehensive narratives.

13 References

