This trial is designed to assess the effect of evolocumab on intima thickness as measured by coronary IVUS. The sample size of the present study is based calculations relating to the primary outcome, the change in maximal intima thickness from baseline to one year. In the SCHEDULE trial, we observed an increase in the maximal intima thickness of 0.08 (SD 0.12) mm in the placebo group, whereas the corresponding increase was 0.03 (SD 0.06) mm in the everolimus arm.² Intensive cholesterol reduction has been shown to actually reverse the atherosclerotic volume in previous trials.³,⁴ We therefore hope to achieve a 0.05 mm between-group difference in the change in the intima thickness in the EVOLVD trial. With an estimated 0.09 mm standard deviation, we will require 51 patients in each arm with a power of 80%, at a two-sided alpha level of 5%. To increase the chances of reaching the primary and secondary outcomes, and to compensate for uncertainties in

this calculation, we will aim for 120 patients to complete the one-year follow-up. To allow for a dropout rate of 5 - 10%, we plan to include 130 patients.

9 General Considerations

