9.4 Missing Data

Because the measurements of the primary endpoint and key secondary endpoints are collected twice only, and the endpoint analyses will be baseline adjusted ANCOVA, there will be no imputation of missing data in the primary analyses, which will be analysed on the FAS. However, to elucidate possible biases this method entails, baseline data (see Section 9.3) for patients for whom endpoint data exist will be tabulated along with baseline data for patients who for some reason drop out or are unable to complete both sets of tests. Any noteworthy differences will be commented on. We will also describe the dropout rate in each treatment arm and comment on any important differences. The extent of missing data will be reported for each endpoint variable.

The impact of missing data for the primary endpoint will be assessed with sensitivity analyses (see Section 10.4).

We expect few missing values on baseline characteristics and will not employ a strategy to impute missing baseline values.

10 Summary of Study Data

[figure not shown]
We will present the baseline characteristics by columns for each treatment (placebo, evolocumab) on the FAS. All continuous variables will be summarised using the following descriptive statistics: mean ± standard deviation; median (interquartile range). The frequency and percentages (based on the non-missing sample size) of observed levels will be reported for all categorical measures.

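### SAP 11.4, Scenarios 1 and 2: fixed imputed changes carry no imputation uncertainty, are centred on the both-arm mean and never shift placebo by an SD, so robustness to missing scans is overstated

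*SAP*

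**What the plan says.** The primary analysis set (SAP 9.2.1) keeps only randomised patients with adequate ultrasound at both baseline and 12 months, and SAP 9.4 rules out imputation in the primary analyses. The same section adds: "The impact of missing data for the primary endpoint will be assessed with sensitivity analyses". Those analyses are in SAP 11.4, which accepts that dropout may not be completely random and may bias the result.

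In Scenarios 1 (best case) and 2 (worst case), a missing evolocumab patient is given the mean change minus or plus 1 SD. In both scenarios, "missing data in the placebo arm are imputed such that the change from baseline to 12 months is equal to the mean change". On the source of these figures: "The mean change and SD are based on all observed values from both the intervention and placebo arms". SAP 11.4 specifies no random draw, no multiple imputation and no variance correction. Scenario 3 is not part of this point.

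**The concern.** Three features of Scenarios 1 and 2 work against their purpose.

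1. Each filled value is the patient's own baseline plus a constant. It enters the model as an observation, so the standard error reflects neither residual scatter nor uncertainty about the imputed value.
2. The constant is centred on the mean of both arms together. Each arm is pulled toward the other before any shift is applied, so the best-to-worst band is not centred on the observed effect.
3. Only evolocumab is shifted by an SD. The scenario labelled worst case omits the adverse movement in placebo, and the best case omits the favourable one.

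At stake is how a positive primary result is described. A reader told that it survived a worst case will take that as a stronger statement than these analyses can support.

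**Working it through.** **Inputs.** From the sample size section (SAP 8): the target effect, "We therefore hope to achieve a 0.05 mm between-group difference in the change in the intima thickness in the EVOLVD trial"; a planning SD of 0.09 mm; in the prior trial, "we observed an increase in the maximal intima thickness of 0.08 (SD 0.12) mm in the placebo group" and "the corresponding increase was 0.03 (SD 0.06) mm in the everolimus arm". Also 130 patients randomised 1:1 (65 per arm) and 120 completing, so the missing fraction is m = 10/130 = 7.7%, or 5 per arm if equal.

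**Assumed, not in the documents.** The SAP 11.2 ANCOVA is fitted after imputation. Baseline SD is 0.25 mm (0.15 also tried), slope on baseline is 1 (0.8 also tried), and missingness is unrelated to outcome. Scenario 1 is read as mean minus 1 SD.

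**The plan's own figure.** n = 2 × (1.960 + 0.842)² × 0.09² / 0.05² = 50.9, so 51 per arm, as stated.

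**Estimates.** Let D = −0.05 mm and s be the both-arm SD of change. With arm SDs 0.12 and 0.06, s = √[(0.0144 + 0.0036)/2 + 0.025²] = 0.098. The scenario estimate is (1 − m)D ∓ m·s.
- Scenario 1: −0.0462 − 0.0075 = −0.0537 mm.
- Scenario 2: −0.0462 + 0.0075 = −0.0386 mm (rounded from unrounded terms).
- Midpoint: −0.0462 mm, not −0.050 mm.
- Within-arm centring, evolocumab +1 SD and placebo −1 SD: D + 2m·s = −0.050 + 0.0151 = −0.0349 mm.

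**Precision (change-score approximation, SD 0.09 in both arms, s = 0.0934).** Filling a fraction m of an arm at distance d from its own mean gives variance (1 − m)σ² + m(1 − m)d².
- Placebo, d = −0.025: 0.00748 + 0.00004 = 0.00752.
- Evolocumab, Scenario 1, d = 0.025 − 0.0934 = −0.0684: 0.00748 + 0.00033 = 0.00781.
- Evolocumab, Scenario 2, d = 0.025 + 0.0934 = 0.1184: 0.00748 + 0.00100 = 0.00847 (rounded).
- SE of the difference: Scenario 1 √(0.01533/65) = 0.01536; Scenario 2 √(0.01599/65) = 0.01569; nothing missing √(0.0162/65) = 0.01579; observed cases √(0.0162/60) = 0.01643.

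**Simulation of the ANCOVA** (1,200 replicates per case, six centres, SD 0.09, equal missingness), 95% interval width in mm:

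| Missing | Observed cases | Scenario 1 | Scenario 2 | Multiple imputation, Scenario 2 shift |
|---|---|---|---|---|
| 0% | 0.0639 | 0.0639 | 0.0639 | 0.0639 |
| 7.7% | 0.0667 | 0.0621 | 0.0635 | 0.0688 |
| 20% | 0.0718 | 0.0587 | 0.0618 | 0.0752 |

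At 7.7%, Scenarios 1 and 2 are 6.9% and 4.8% narrower than observed cases, and 9.7% and 7.7% narrower than the multiple-imputation column. At 20% they are 18% and 14% narrower than observed cases. The 20% row is an assumption beyond the planned dropout.

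**Where Scenario 2 does not narrow.** With 15% missing in evolocumab only, its width is 0.0651 against 0.0638 with nothing missing. With slope 0.8 and 10% missing it is 0.0645 against 0.0638. The reason is visible in the formula: the +1 SD shift puts the filled values far enough from their arm mean to replace most, or more than all, of the variance they remove. Both widths are still below the observed-case ones (0.0668 and 0.0672). Scenario 1 was below the no-missing width in every setting run.

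**Share still significant, 7.7% missing per arm, true difference −0.05 mm.** With arm SDs 0.12 and 0.06, about 60–64% for Scenario 2, against about 45–47% for within-arm multiple imputation with opposing 1 SD shifts (mean estimates about −0.038 and −0.034 mm). With SD 0.09, adding imputation noise alone, at the same Scenario 2 shift and estimate, lowers the share from 68% to 63%.

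**The case against.** A reader might infer that the scenario intervals always become tighter than those of a trial with no missing scans. That does not follow for Scenario 2, the one that tests a positive result: the settings above include two where it is slightly wider, and at planned dropout with slope 1 it is under 1% narrower.

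A reader might also infer that the worst case is far too mild. The pooled centre counts against that. Under the planned effect it already moves missing placebo patients 0.025 mm below their arm mean and missing evolocumab patients 0.025 mm above theirs. The total adverse shift is 0.098 + 0.050 = 0.148 mm, about 75% of the 0.196 mm in the opposing-shift version. That is why the estimates differ by less than 0.004 mm at 7.7% missing. The same pull understates the favourable side, which is conservative in a superiority trial.

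Further, SAP 11.4 does not expect treatment to affect dropout, a one-arm shift is a recognisable stress test, and opposing 1 SD shifts are no absolute bound either. SAP 9.4 also requires baseline comparisons and dropout by arm. The decision rule in SAP 11.1 uses only the primary p-value, so no claim of superiority turns on these scenarios.

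All of this limits the size of the point. It does not remove it: the interval is narrower than the observed-case interval in every setting run, no scenario shifts placebo by an SD, and the SAP 9.4 comparisons are descriptive and cannot quantify bias in the treatment effect.

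**Conclusion.** The point stands as an overstatement of robustness, not as a fault in the primary test. At the planned 7.7% missing, equal in both arms, the Scenario 1 and 2 intervals are about 5–7% narrower than the observed-case interval and about 8–10% narrower than delta-adjusted multiple imputation. The best-to-worst band is centred near −0.046 mm rather than the planned −0.050 mm. About 60–64% of Scenario 2 analyses remain significant, against about 45–47% when both arms are moved.

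These sizes rest on the planned effect and SDs, an assumed baseline SD of 0.25 mm and an assumed slope of 1. They grow with more missing data. The contrast from moving placebo disappears if scans are missing in evolocumab only and the pooled centre is kept. The change is worth making before the code is opened, because SAP 11.4 is the plan's only quantitative check on missing primary data.

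**What to change.** Replace Scenarios 1 and 2 with delta-adjusted multiple imputation:

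- Impute the 12-month thickness separately within each arm from baseline thickness and centre, with at least 20 imputations.
- Add delta = −1, 0 and +1 times the pooled observed SD of change to the imputed values in each arm, including the opposing combinations.
- Fit the SAP 11.2 ANCOVA to each completed data set and pool by Rubin's rules.
- Name delta = 0 in both arms as the neutral analysis, and evolocumab +1 SD with placebo −1 SD as the worst case.
- Apply this to patients with a usable baseline scan, and report those without one separately.

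The cost is SAP wording and a little code; no new data, visits or patients are needed. The downside for the sponsor is wider sensitivity intervals and a less favourable worst case.

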7.5 Study Variables

7.5.1 Primary endpoint:

The primary endpoint, the maximal intracoronary intima thickness, is measured as the largest distance from the intimal leading edge to the external elastic membrane on matched slices of the same coronary vessel (Figure 1). All intracoronary ultrasound analyses will be conducted after trial closure at a core laboratory (Oslo University Hospital, Rikshospitalet, Oslo, Norway) by personnel blinded to patient treatment. Precise matching of the IVUS recordings at baseline and at 12 months will be performed and contour detection of both the lumen and external elastic membrane will be performed at approximately 1 mm intervals using validated software (QIVUS, v.3.0, Medis medical imaging systems, Leiden, the Netherlands). Borders will be reviewed by two independent operators according to the guidelines for acquisition and analysis of intravascular ultrasound (IVUS) images by the American College of Cardiology and European Society of Cardiology.

Figure 1

[figure not shown]

Illustration of single slice of coronary ultrasound images. Multiple slices are recorded at constant intervals along a coronary vessel and matched (baseline/follow-up) for direct comparison. The primary endpoint of the trial is the maximal intima thickness, measured from the external elastic membrane (EMM) to the luminal border. The percent atheroma volume is the percentage of the intima area (EMM area – lumen area) that contains lipids (different echogenicity than the healthy intimal area) across the entire matched segment of the coronary artery. (E From Stephen J. Nicholls et al, Relationship Between Cardiovascular Risk Factors and Atherosclerotic Disease Burden Measured by Intravascular Ultrasound. JACC 2006:47;1967-75.

7.5.2 Secondary endpoints:

The secondary endpoints "percent atheroma volume" and "cardiac allograft vasculopathy" will be analysed on matched sections of the IVUS images of the coronary vessel with contour detection of the lumen and external elastic membrane for each mm. "Percent atheroma volume" expresses the summation of atheroma areas in proportion to the area between the lumen and the external elastic membrane (in percent) (Figure). "Cardiac allograft vasculopathy" is defined as the extent to which the mean maximal intimal thickness is ≥0.5 mm over the entire matched segment.

8 Sample Size

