9.2 Populations for analysis

9.2.1 Full analysis set (modified intention-to-treat population)

The full analysis set (FAS) will include all patients who were randomised and who (irrespective of receipt of actual treatment) had intracoronary ultrasound adequate for the determination of coronary intima thickness at baseline and at the 12 months follow-up. The adequacy of the ultrasound examination must be determined before database lock and the randomisation code is opened. The primary analysis of the primary endpoint (and all secondary endpoints) will be carried out on the FAS.

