11.2 Continuous endpoints measured at two points in time

Continuous variables measured at baseline and 12 months' follow-up only, including the primary endpoint, percent atheroma volume, and cardiac allograft vasculopathy, will be performed as analysis of covariance (ANCOVA) in the full analysis set. The model will be a linear regression with

the 12 months' follow-up measurement as the outcome (dependent) variable and treatment allocation (0=placebo, 1 = Evolocumab), baseline value, and centre (stratification factor in the randomisation) as explanatory (independent) variables. The effect measure will be the beta-coefficient for treatment allocation (the between-group difference), estimated with a 95% confidence interval. For the primary endpoint only, we will also report the two-sided p-value for the null hypothesis of a zero-treatment effect.

The observed data and the estimated between-group difference from the ANCOVA analyses will be illustrated with the regression lines for placebo and Evolocumab superimposed on a scatter plot of the baseline measurements (x-axis) and the 12-months follow-up measurements (y-axis).

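### SAP 11.4 Scenario 3 is labelled no-change but imputes a pooled mean value, so the implied change is about +0.055 mm and any observed baseline is ignored

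*SAP*

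**What the plan says.** The primary ANCOVA regresses the 12-month value on treatment, with "baseline value, and centre (stratification factor in the randomisation) as explanatory (independent) variables" (SAP 11.2). It is fitted to the full analysis set, whose members "had intracoronary ultrasound adequate for the determination of coronary intima thickness at baseline and at the 12 months follow-up" (SAP 9.2.1). SAP 9.4 adds that "there will be no imputation of missing data in the primary analyses, which will be analysed on the FAS" and refers the impact of missing primary-endpoint data to sensitivity analyses. Protocol 10.5 likewise omits missing values.

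SAP 11.4 concedes that "it is unreasonable to assume that dropouts will occur completely at random" and continues: "We therefore aim to do best-case, worst-case, no-change scenario imputations for missing data".

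- Scenarios 1 and 2 are defined on the change from baseline. Missing evolocumab patients get the pooled mean change minus 1 SD (best case, as I read it) or plus 1 SD (worst case). Missing placebo patients get the pooled mean change.
- Scenario 3, the no-change case, is defined on the value: "all missing data in intervention and placebo arms are imputed as the overall (i.e., both treatment arms combined) mean observed value at each time point".

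Neither document defines no-change in any other way.

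**The concern.** The label and the rule describe different things. No change would mean a 12-month value equal to the patient's own baseline. The rule gives every missing patient the same 12-month value, whatever the baseline. Under a model that conditions on baseline, a patient who started thick is thereby given regression and one who started thin is given progression.

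The three scenarios are the plan's only quantitative check on a complete-case primary analysis. If Scenario 3 came out worse than the worst case, the result would look fragile; if better than the best case, unusually robust. Either could come from the imputation rule alone and not from any assumption about the lost patients.

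**Working it through.** **Inputs from SAP 8.** Change 0.08 (SD 0.12) mm in the control arm and 0.03 (SD 0.06) mm in the active arm; target difference 0.05 mm; planning SD 0.09 mm; 130 enrolled, 120 completing, dropout 5-10%.

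**Assumed, because the documents do not give them.** 65 per arm, six equal centres, 6 missing per arm (12/130 = 9.2%), a slope of 1 for the 12-month value on baseline, and baseline SD over a range.

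**1. The plan's own figure.** n per arm = 2(1.960 + 0.842)² × 0.09² / 0.05² = 50.9, so 51. This reproduces. The SAP states no numerical result for the scenarios.

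**2. Implied change in Scenario 3.** It equals the pooled 12-month mean minus own baseline. With equal, random dropout it averages (0.08 + 0.03)/2 = +0.055 mm, slightly more than the target effect. For a single patient it falls one-for-one as baseline rises.

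**3. Width of the Scenario 1-2 band.** Pooled SD of change = √[(0.12² + 0.06²)/2 + 0.025²] = 0.098 mm, where 0.025 is half the arm difference. Moving 6 of 65 evolocumab patients by this amount moves the arm mean by 0.098 × 6/65 = 0.0090 mm, the half-width. The midpoint is own baseline + pooled mean change in both arms.

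**4. Distance of Scenario 3 from that midpoint.** Let Δ be the mean baseline of the missing evolocumab patients minus that of the missing placebo patients. The coefficient shifts by about -0.083 × Δ (simulated; 6/65 = 0.092 before allowing for the flatter fitted slope). Scenario 3 leaves the band once |Δ| exceeds 0.0090/0.083 ≈ 0.11 mm. Under random dropout the SD of Δ is baseline SD × √(2/6). A normal approximation then gives about 6%, 21% and 45% outside at baseline SD 0.10, 0.15 and 0.25 mm.

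**5. Simulation of the SAP 11.2 model, random dropout, 6 per arm.**

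| Assumed baseline SD (mm) | Scenario 3 outside the Scenario 1-2 band |
|---|---|
| 0.05 | 0.1% |
| 0.10 | 7% |
| 0.15 | 23% |
| 0.25 | 48% |

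Excursions fall about equally on each side. Averaged over trials, Scenario 3 is about -0.045, inside the band. At SD 0.25 its standard error is 0.0204, against 0.0175 for complete cases.

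**6. Dropout related to baseline in one arm (illustration).** Take SD 0.15 and evolocumab dropouts about 0.9 SD thicker or thinner at baseline than average. Scenario 3 then averages about -0.058 or -0.033, against a band of -0.054 to -0.036. The complete-case estimate stays near -0.050.

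**7. The other reading of the rule.** If both the baseline and the 12-month value of a missing patient are set to pooled means, that patient sits at the centre of the data. At slope 1, Scenario 3 is then outside the band in 0% of runs. The implied change is still +0.055 mm.

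**8. The two candidate replacements.** Own baseline + pooled mean change is always inside the band, being its midpoint. True zero change differs from that midpoint by 0.055 × (difference in numbers missing)/65.

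- Equal dropout: the difference is zero.
- 3 evolocumab and 9 placebo missing: 0.055 × 6/65 = 0.0051, against a half-width of 0.098 × 3/65 = 0.0045. It is outside in about 70% of runs.
- 9 evolocumab and 3 placebo missing: the half-width is 0.098 × 9/65 = 0.0136, so it stays inside (-0.051, against -0.045 for pooled mean change).

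**The case against.** The strongest reply is that the frequencies rest on an input the plan does not contain. That stands. At a baseline SD of 0.05 mm excursions are negligible, and nothing in the documents supports 0.25 mm over 0.05 mm. The excursions under random dropout are also modest: the median overshoot is 0.0014, 0.0030 and 0.0058 mm at SD 0.10, 0.15 and 0.25, against a complete-case standard error of 0.0175.

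Second, a reader might infer that Scenario 3 was meant as the neutral case lying between best and worst. The SAP never says so. Scenarios 1 and 2 shift only the evolocumab arm, and true zero change can itself leave their band. Falling outside is therefore not a breach of the plan; the defect is that the rule does not do what its label says.

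Third, a reader might infer that missing baselines will certainly be filled in. The wording on each time point allows this, but SAP 9.4 says missing baseline characteristics will not be imputed. How far that sentence reaches is arguable, so this is a tension to resolve. The endpoint is "measured as the largest distance from the intimal leading edge to the external elastic membrane on matched slices of the same coronary vessel" (SAP 7.5.1), so a patient with no second recording has no matched segment and perhaps no endpoint baseline. That makes the both-values reading possible, and under it the excursions disappear. Against it, Scenarios 1 and 2 presuppose a usable baseline for the same patients.

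Finally, SAP 9.4 also tabulates baseline data for patients with and without endpoint data and reports dropout by arm. This helps a reader notice an imbalance but does not correct the estimate.

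**Conclusion.** The label and the rule disagree. The implied change of about +0.055 mm follows from the plan's own figures, given equal and random dropout. Where baseline is observed, discarding it makes the estimate depend on which patients happen to be lost. That dependence is certain in direction but not in size: anything from negligible to about half of trials over baseline SDs of 0.05 to 0.25 mm, with 6 missing per arm and slope 1.

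It would go too far to conclude that the trial's result is at risk. The effect measure and decision rule in SAP 11.1 and 11.2 do not use Scenario 3, and Scenarios 1 and 2 remain usable bounds for the point estimate. The point should still be corrected, because the correction is short and this sensitivity analysis is meant to show robustness under dropout that the SAP itself does not take to be completely random.

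**What to change.** Before unblinding, define Scenario 3 from the patient's own baseline and make the label match. Choose one:

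- **Own baseline + pooled mean change in both arms**, relabelled, for example, no arm-specific shift. It always lies within Scenarios 1-2, but as their exact midpoint it adds little new information.
- **Own baseline, true zero change**, keeping the label. State that this is a separate assumption that can fall outside Scenarios 1-2 when dropout is unequal.

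Also state which baseline value is used when there is no matched segment, for example the full analysable baseline recording; Scenarios 1 and 2 need the same definition. State that patients with no usable baseline are left out of this scenario, which removes the tension with SAP 9.4.

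The cost is a few sentences in the SAP and no new data. The downside is that patients without a usable baseline drop out of the scenario.
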